[name], Co-Investigator, Washington University
Department of Occupational Therapy, [name],
[name] [contact], [contact]

University of Illinois at Chicago Team Members

[name], Co-Investigator, University of Illinois at Chicago
Department of Occupational Therapy, [name],
[name] [contact], [contact]

[name], Co-Investigator, University of Illinois at Chicago
Department of Occupational Therapy, [name],
[name] [contact], [contact]

[name], Co-Investigator, University of Illinois at Chicago
Department of Occupational Therapy, [name],
[name] [contact], [contact]

University of Pittsburgh Peer Mentor
[name], Pittsburgh, PA

Washington University Peer Mentors
[name], St. Louis, MO

PRÉCIS

Study Title

ENGAGE: Promoting Participation and Health in People with Stroke-Related Disability

Objectives

The objectives of this study are to examine the feasibility, acceptability, and safety of a multi-site implementation of ENGAGE and to describe change in community participation among adults with stroke-related disability and low income.

Design and Outcomes

This is a multi-site, multi-phase (in-person, remote), single-arm community-based pilot study examining the feasibility, acceptability, safety, and estimated effects of ENGAGE. Indices of intervention feasibility, acceptability, and safety will be assessed. Community participation and measures of physical, social and emotional health will be administered before and after the intervention.

Interventions and Duration

All participants will receive a 6-week (12 sessions, 2 times per week) self-management intervention with social learning (group training) and guided skill development (individual application).

Sample Size and Population

Participant will have mild to moderate stroke-related disability for a minimum of 3 months and identified limitations in community participation.

1. STUDY OBJECTIVES

1.1 Primary Objective

The primary objective of this study is to examine the feasibility, acceptability, and safety of a multi-site, multi-phase implementation of ENGAGE to address community participation among adults with stroke-related disability and low income. We will partner with Washington University Community Research Fellows and the University of Pittsburgh Community PARTners to adapt and implement the intervention to address the needs of people with mild to moderate stroke-related disability and low income who live in Pittsburgh, St. Louis, and Chicago. We will clarify and describe the specific adaptations necessary to support this population. We will test this intervention through in-person and remote delivery methods. Feasibility will be indicated by >90% of target enrollment, >90% retention, and >90% intervention fidelity at each site; acceptability will be indicated by >90% participant satisfaction at each site; and safety will be indicated by <3% participants with a reportable event (i.e., injurious fall) at each site.

1.2 Secondary Objectives

The secondary objective of this study is to describe intervention response among

participants at each site, indicated by pre-post change in PROMIS Ability to Participate in Social Roles and Activities. We will also explore changes in satisfaction with participation (PROMIS Satisfaction with Participation in Social Roles and Activities), physical activity (step count/day), sedentary behavior (sitting time/day), social (PROMIS Social Isolation), and perceived health (PROMIS-29) to inform future studies.

2. BACKGROUND AND RATIONALE

2.1 Background on Condition, Disease, or Other Primary Study Focus

Significant advancements in acute medical management have shifted stroke from an acute condition with a high prevalence of mortality to a chronic condition with high prevalence of morbidity. One of the leading causes of chronic illness and disability worldwide, stroke results in residual impairments in sensorimotor, cognition, and communication impairments. These impairments reduce over time, but few people have complete restoration of function. Hence, people with stroke-related disability do not resume pre-stroke levels of community participation (education; paid or volunteer work; civic, social, and religious activities; and leisure). Low levels of community participation are associated with inactivity, sedentary behavior, and social isolation, each contributors to cardiovascular disease, diabetes, obesity, pulmonary conditions, depression – and secondary stroke. These consequences are particularly problematic for people with low income who have limited resources.

It may be possible to improve community participation after stroke, despite residual disability. Unfortunately, interventions remain under-developed and under-studied. Thus, the NIH Research Plan on Rehabilitation identifies this as one of the critical focus areas for rehabilitation research. We need community-focused and individually-tailored, and culturally-responsive interventions to promote community participation, particularly in portions of the population most vulnerable to poor health outcomes.

2.2 Study Rationale

Our team of occupational therapy scientists has designed ENGAGE, a self-management training program that uses social learning and guided discovery to help people with mild to moderate stroke-related disability resume community participation, and to develop a strong network of social support. Our previous research demonstrates that self-management training with social learning results in significantly greater gains in self-efficacy for community participation, as well as improved “enfranchisement” (a sense of belonging) compared to a wait-list control group. That is, participants felt more confident and more integrated and valued in the community after the intervention (Cohen’s $d=1.45$). Additional research demonstrates that guided skill development helps people with stroke-related cognitive impairments 1) identify and solve problems in everyday activities, and 2) achieve greater improvements in independence (Cohen’s $d=1.06$) and executive functions (Cohen’s $d=1.38$) compared to usual rehabilitation practices. Guided skill development teaches people how to identify problematic daily activities and barriers, and generate and evaluate their own strategies to address barriers. Instructors facilitate learning through

prompts and questions, rather than directly instructing participants. We posit that self-management training with social learning and guided skill development may comprise the optimal program to promote improved frequency and satisfaction with community participation, and subsequently improve overall health.

However, the combination of these elements has yet to be studied in people with chronic stroke-related disability who live with low income – one of the most vulnerable segments of the population. By partnering with the Community Research Fellows Program at Washington University and the Community PARTners Program at the University of Pittsburgh, this multisite team seeks to design and implement a culturally-responsive program to promote community participation among people with stroke-related disability and low income. This new collaboration is the next logical step in the development and examination of community-based interventions to promote self-management and community participation after stroke.

The self-management training will be administered by an occupational therapist and a peer-mentor in group sessions (social learning). Individual application of the self-management training content will be facilitated with guided skill development principles. The intervention will be 12 two-hour sessions, offered 2 times per week for 6 weeks, based on previous intervention dosing studies. There are limited known and potential risks because the intervention focuses on doing routine daily activities in the home and the community, as would normally be encountered in the course of everyday life. However, there is a minimal risk of frustration fatigue, fall, or injury that may result from increasing physical and social activity levels over the course of time. These risks will be minimized through supervision of licensed occupational therapists.

ADDENDUM: With the onset of the pandemic, we developed methods to deliver this intervention program remotely. People with stroke-related disability, particularly those in low income communities, face unique problems in the home and the community during pandemic conditions. We decided to add a second phase of the study, delivering the intervention remotely, to address these needs, and to compare metrics across phases (in person, remote).

3. STUDY DESIGN

This is a multi-site, multi-phase single-arm community-based clinical trial examining the feasibility, acceptability, safety, and variation in changes in community participation attributed to ENGAGE among community-dwelling adults with mild to moderate stroke-related disability and low income. The 6 week intervention (12 two-hour sessions, 2 times per week) intervention will be delivered in community-based settings (in person) or in the home (remote), and assessments will be delivered in the home or community-based settings (in person) or via teleconference (remote). Assessments will be administered by independent evaluators at each site, and all data will be collected electronically and stored in REDCap, a cloud-based data management system accessible to all investigators at all sites.

4. SELECTION AND ENROLLMENT OF PARTICIPANTS

4.1 Inclusion Criteria

Inclusion criteria are: 1) ages 18 and older, 2) chronic stroke (minimum 3 months), 3) community-dwelling, 4) mild to moderate stroke-related disability (NIHSS ≥ 16), 5) restrictions in community participation (Activity Card Sort indicates retention of <80% of pre-stroke community participation activities), 6) low income (uninsured or underinsured), and 7) able to provide written informed consent.

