4.2 Exclusion Criteria

Exclusion criteria are: 1) currently receiving rehabilitation services, 2) dementia diagnosis, 3) severe aphasia (0 or 1 on the Boston Diagnostic Aphasia Examination Severity Rating Scale), 4) current major depressive, bipolar, or psychotic disorder (PRIME-MD), or 5) substance abuse within 3 months (Mini-International Neuropsychiatric Interview).

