4.3 Study Enrollment Procedures

We will recruit research participants from stroke and rehabilitation research registries and stroke recovery support groups. Interested participants will be encouraged to contact the study team by telephone or email, and the study team will follow up with an initial phone call using the approved recruitment script. If the potential participant provides verbal consent as per approved procedures, the study team will describe the purpose of the study, the procedures involved and the potential risks and benefits of study participation. Persons providing written or electronic informed consent will be asked to describe the study in their own words to ensure their understanding. In addition, persons providing informed consent will be invited to ask questions about the research study and will be provided time to think about study participation, prior to providing informed consent. Even after informed consent is obtained, participants will be invited to ask questions about the study and ongoing participation. All of these procedures will be documented in the research record via tablet and uploaded to REDCap, the cloud-based data management system.

All contacts with potential research participants will be documented in the screening log maintained in REDCap. Potential participants who do not provide informed consent or are ineligible will be identified by a code (NC1, NC2) and the reason for non-participation or ineligibility will be maintained. No identifiers will be maintained or linked to these codes. Participants who do provide informed consent will be identified by their assigned study identification code (with a linking file maintained separately). Study identification codes will be assigned through REDCap.

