6. STUDY PROCEDURES

6.1 Schedule of Evaluations

Assessment	Screening: (Day -14 to -1)	Pre- Intervention (Day -14 to -1)	Intervention Sessions (Day 0 to 42)	Post- Intervention (Day 43 to 57)
Referral Log				
Informed Consent				
Screening Assessments	X			
Screening Checklist	X			
Participant Characteristics		X		
Comorbidity Questionnaire		X		
Cognitive Assessment		X		
Social Support Survey		X		
Ability to Participate		X		
Satisfaction with Participation		X		X
Social Isolation		X		X
Global Health		X		X
Community Participation		X		X
Participation Activation		X		X
Participation Self-Efficacy		X		X
Patient Activation		X		X
Chronic Disease Self-Efficacy		X		X
Sedentary Behavior		X		X
Physical Activity Scale		X		X
ActivPal		X		X
Intervention Record			X	

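### Inclusion criterion 4 labels the population mild to moderate but, as printed, sets an NIHSS floor of 16 with no ceiling

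*Combined protocol and SAP*

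**What the plan says.** The fourth inclusion criterion in section 4.1 gives the severity requirement as "mild to moderate stroke-related disability (NIHSS ≥ 16". This is the only NIHSS value in the combined protocol and SAP.

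The verbal label recurs wherever the population is described:

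- Précis, Sample Size and Population: "Participant will have mild to moderate stroke-related disability for a minimum of 3 months".
- Section 1.1, Primary Objective: "people with mild to moderate stroke-related disability and low income who live in Pittsburgh, St. Louis, and Chicago".
- Section 2.2, Study Rationale: the programme is meant to "help people with mild to moderate stroke-related disability resume community participation".
- Section 3, Study Design: "community-dwelling adults with mild to moderate stroke-related disability and low income".

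Section 4.2 contains no NIHSS limit. Its exclusions that bear most directly on stroke severity are a dementia diagnosis and "severe aphasia (0 or 1 on the Boston Diagnostic Aphasia Examination Severity Rating Scale". Section 6.2.1 describes the NIHSS as a measure of neurological impairment after stroke, without stating its range, its direction or any severity bands.

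**The concern.** A label of mild to moderate implies an upper limit on severity. The number attached to it is a lower limit with nothing above it. If a higher NIHSS score means more impairment, the two halves of the criterion point in opposite directions.

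This is the threshold that decides who enters the study, so both ways of resolving it in practice cause trouble:

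- **The number is followed.** The trial enrols people scoring 16 and above, and its feasibility, acceptability, safety and change results do not answer the question in section 1.1. The site-level benchmarks leave little slack: at the planned minimum of 20 per site, one participant with a reportable event is 1/20 = 5%, already over the 3% limit. Who was eligible therefore bears directly on how such a result is read.
- **The label is followed.** Anyone enrolled with a score below 16 was enrolled against the written criterion. On the ordinary meaning of a deviation, each such case falls under section 10.3.2, which requires immediate reporting to the IRB.

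Sites might also read the criterion differently from one another, but nothing in the documents shows this. The shared REDCap database (section 10.1), weekly Executive Committee review (section 10.3.3) and single IRB (section 11.1) make it less likely.

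**Working it through.** **Inputs.** From section 4.1: the label (mild to moderate) and the rule (NIHSS at or above 16). From section 9.2: n = 60, d = 0.37, two-tailed paired t-test, α = 0.05, 80% power. Assumed, because the documents do not give it: NIHSS scored in whole numbers from 0 to 42, higher meaning more impairment.

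**Step 1. The plan's own figure.** The only computed design figure is the power statement. With df = 59 and noncentrality d√n = 0.37 × √60 = 2.87, the noncentral t distribution gives power 0.805, and the effect detectable at 80% power is d = 0.368. The stated 80% and 0.37 reproduce. No NIHSS term enters the calculation, so the criterion does not affect it.

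**Step 2. What the rule admits.**

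| Set | Scores | Count |
|---|---|---|
| All possible | 0 to 42 | 43 |
| Admitted as printed | 16 to 42 | 42 − 16 + 1 = 27 |
| Excluded as printed | 0 to 15 | 43 − 27 = 16 |

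The excluded scores are the 16 lowest, which on the assumed direction are the mildest. The admitted set runs to the top of the scale. No severity bands are needed for this conclusion: an open-ended floor above zero drops the mildest scores and keeps the most severe.

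**Step 3. Effect of the sign.** The same number with the opposite sign would admit 0 to 16, which is 17 scores. This is shown only to size the effect of the sign and is not a proposed rule. The two readings share one score (16) and differ on 26 + 16 = 42 of 43. With a top score of 30 they differ on 30 of 31, and with 50 on 50 of 51. Reversing any inclusive inequality leaves exactly one shared score, so this count only shows that the sign decides almost everything. It is a count of scores, not of people.

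**Step 4. Dependence on direction.** If higher meant less impairment, a floor would fit the label and the point would fall. The documents state no such reversed scoring.

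**Step 5. Could another criterion repair it?** Living in the community and being able to consent (section 4.1), and the dementia and severe aphasia exclusions (section 4.2), may remove some severely impaired people. None of them caps the NIHSS, and none can readmit someone scoring below 16, because every inclusion criterion must be met.

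**The case against.** The strongest case is that this is one symbol in one line, and probably a typographical slip.

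- **Scale direction.** The contradiction rests on a direction that the documents do not print. That is true, and it is stated as an assumption. It is a basic property of a named instrument, and once it is granted no severity bands are needed.
- **Reading error.** The sign occurs only once in the text, so it cannot be checked against another use, and a misread of the PDF is possible. This stands. Confidence is high for the printed text, not for the approved protocol. Nothing in the documents positively suggests a reading fault at this point.
- **Practical effect.** Recruitment is from registries and support groups, interested people contact the team themselves, and those consenting describe the study in their own words (section 4.3). The intervention consists of two-hour group sessions with workbooks (section 5.1). All this makes a sample running from 16 to the top of the scale less plausible, and the documents do not show what was applied at screening. That limits the likely effect but does not repair the rule, since people scoring below 16 remain ineligible as written.
- **Timing.** The addendum in section 2.2 shows that a remote phase was added after the pandemic began, so enrolment may be well advanced and an amendment may come late. The documents do not say. The source check and the comparison of enrolled scores are useful either way.

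**Conclusion.** The concern holds for the text as printed. This is an internal contradiction in a core eligibility rule, and it must be fixed unless the approved source already agrees with the label.

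The size that matters is that the 16 lowest of 43 scores are ruled out and no NIHSS ceiling is set. The number of candidates affected cannot be estimated, since the documents give neither an NIHSS distribution nor severity bands. The consequence is for whom the feasibility, acceptability, safety and change results describe, and for whether enrolled participants met the written criterion. The sample-size calculation does not change.

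The conclusion rests on two conditions: that a higher NIHSS score means more impairment, and that the sign shown is the sign in the approved protocol.

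**What to change.** 1. Check the sign and the value in criterion 4 against the approved source protocol. If the approved text agrees with the label, the point closes.
2. If it reads as printed, amend criterion 4 through the single IRB (section 11.1) so that the numeric rule and the label agree. The sponsor sets the direction and the cut-off; this review proposes neither. State the NIHSS range and direction in section 6.2.1 at the same time.
3. Bring the "Screening Checklist" listed in section 6.1 into line with the reconciled rule.
4. Compare the NIHSS scores of everyone already enrolled with the reconciled rule.
5. Report how many people were turned away on NIHSS. The screening log should support this, since section 4.3 says that "the reason for non-participation or ineligibility will be maintained".

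The cost is a source check and, if the printed text is confirmed, a short amendment and a review of screening records already held. No participants or procedures are added.

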4.2 Exclusion Criteria

Exclusion criteria are: 1) currently receiving rehabilitation services, 2) dementia diagnosis, 3) severe aphasia (0 or 1 on the Boston Diagnostic Aphasia Examination Severity Rating Scale), 4) current major depressive, bipolar, or psychotic disorder (PRIME-MD), or 5) substance abuse within 3 months (Mini-International Neuropsychiatric Interview).

4.3 Study Enrollment Procedures

We will recruit research participants from stroke and rehabilitation research registries and stroke recovery support groups. Interested participants will be encouraged to contact the study team by telephone or email, and the study team will follow up with an initial phone call using the approved recruitment script. If the potential participant provides verbal consent as per approved procedures, the study team will describe the purpose of the study, the procedures involved and the potential risks and benefits of study participation. Persons providing written or electronic informed consent will be asked to describe the study in their own words to ensure their understanding. In addition, persons providing informed consent will be invited to ask questions about the research study and will be provided time to think about study participation, prior to providing informed consent. Even after informed consent is obtained, participants will be invited to ask questions about the study and ongoing participation. All of these procedures will be documented in the research record via tablet and uploaded to REDCap, the cloud-based data management system.

All contacts with potential research participants will be documented in the screening log maintained in REDCap. Potential participants who do not provide informed consent or are ineligible will be identified by a code (NC1, NC2) and the reason for non-participation or ineligibility will be maintained. No identifiers will be maintained or linked to these codes. Participants who do provide informed consent will be identified by their assigned study identification code (with a linking file maintained separately). Study identification codes will be assigned through REDCap.

5. STUDY INTERVENTIONS

5.1 Interventions, Administration, and Duration

The intervention, ENGAGE, will be delivered by trained occupational therapists and peer mentors. Therapists and mentors will deliver the 12 intervention sessions (2 sessions per week for 6 weeks) to groups of 6 to 8 participants, at a university-owned

or community center (in person) or via teleconference with provided technology and internet access (remote). Each session will be 2 hours and will be video recorded.

The intervention blends self-management training with social learning and guided skill development to promote community participation after stroke-related disability. For this project, ENGAGE will be tailored to the needs of people with low income who may have few resources or supports.

Self-management training sessions comprise 12 topics (building community participation plans, understanding the stroke experience, engaging in the community, advocating for self and others, using social networks, strategies for participation, staying active and well, civic and volunteer activities, applying what we learned, sharing what we learned). During each of these sessions, therapists and mentors will use social learning and guided skill development principles to aid participants in identifying individual and collective goals, addressing these goals, and debriefing to support application. Participants will use the Activity Card Sort (published standardized tool with photos of activities in the home and community, sorted by importance to the participant) and workbooks to guide these activities during and between sessions. Refer to the intervention manual for specific procedures.

